5.1.2 Suspected PE

The research nurse or an appropriate trained clinician will complete a data collection form incorporating standard clinical assessment. Participants will undergo diagnostic imaging according to local protocols. At 30 days after recruitment the research nurse will review hospital records and record details of any adverse events and the results of diagnostic investigations for PE. All participants, except those who have died or withdrawn from the study, will be sent a questionnaire by mail or email, or administered over the telephone, to record any additional adverse events, health care received and health utility on the EQ5D.

Where incomplete or indeterminate data impacts the ability of researchers to rule out a PE and additional adverse events, the clinical team at the participating site will contact the patient's GP on behalf of the study to obtain further data from the 30 days immediately post consent related to Suspected PE. A data collection form will be posted to the GP for completion with a photocopy of the participant consent form and participant information sheet.

5.1.3 Non-recruited Suspected PE

As we recognise the difficulty in recruiting in an emergency setting, we will collect baseline non-identifiable data from the case notes of those women who were eligible but were not asked to participate in the study to see how representative the sample of recruited women are.

5.1.4 Diagnosed DVT

The research nurse or an appropriate trained clinician will complete a data collection form incorporating standard clinical assessment.

5.1.5 Lost to follow up procedures

Participants will receive up to 3 reminders to complete the 30-day questionnaire. One of the two reminders will if possible use an alternative method of contact (e.g. phone if no response to mail).

5.1.6 Data collection windows

The data collection windows for the 30-day questionnaire are between and inclusive of day 23 and day 60.

Blood samples are to be taken prior to hospital discharge.

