Measurement of costs and outcomes: The nominated clinician for UKOSS will collect data from women with diagnosed PE detailing clinical variables, blood tests results, diagnostic imaging, treatment and adverse events. Research nurses will collect standardised clinical data and a blood sample at enrolment from women with suspected PE and review hospital records at 30 days to record the results of diagnostic imaging, treatment and adverse events. A questionnaire will then be sent to record adverse events, health care use and health utility. Two independent assessors, blind to clinical predictors and blood results, will classify participants as having PE using diagnostic imaging results and details of serious adverse events.

Sensitivities and specificities of clinical predictors, biomarkers and diagnostic strategies will be estimated using data from cases and controls respectively. Decision-analysis modelling will be used to estimate costs incurred and expected outcomes from thromboembolism, bleeding and radiation exposure if a hypothetical cohort of pregnant or postpartum women were investigated for suspected PE using different strategies, including no imaging, selective imaging and imaging for all. Outcomes will be modelled to estimate the quality-adjusted life years (QALYs) accrued by each strategy and the incremental cost per QALY gained by each strategy compared to the next most effective alternative.

Sample size: Data will be collected from 150 women with diagnosed PE and 325 women with suspected PE, resulting in about 155 cases and 319 controls. This will allow estimation of sensitivity or specificity of 90% with standard errors of about 2.5% and 2.0% respectively.

Project timetables including recruitment rate:

Months 1-6: Preparation, ethics and R&D approval, finalise data collection

Months 7-24: Primary data collection from UKOSS cases (all UK hospitals) and women with suspected PE (8 hospitals, 25 per hospital per year), development of the model

Months 25-30: Follow-up, analysis, modelling and writing-up

Expertise in team: The team includes international experts in obstetric medicine, haematology, epidemiology, emergency medicine, vascular radiology, health economic modelling and statistics.

1. Introduction

Background and Rationale

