- (4) Aged <16 years

Inclusion Criteria- Diagnosed DVT

(1) Pregnant, or post-partum (defined as within 6 weeks of the end of a pregnancy beyond the first trimester) with a diagnosis of DVT confirmed by imaging (Ultrasound or venography)

Exclusion criteria- Diagnosed DVT

- (1) Women with suspected PE (who should be included as suspected PE)
- (2) Women who have been diagnosed with PE or DVT earlier in the current pregnancy and are currently receiving treatment
- (3) Women who are unable or unwilling to provide informed consent
- (4) Aged <16 years

Sampling and Informed Consent

Diagnosed PE: The sampling method has been successfully used in a previous study (Knight 2008). Nominated clinicians in each consultant-led maternity unit in the UK will be sent a card each month and asked to report all cases of antenatal or postnatal PE, thus covering the entire cohort of UK births. To ensure all cases are identified, we will independently contact all radiology departments and ask them to report any cases of PE in pregnant women, providing only their year of birth and date of diagnosis. If a case is identified which has not been reported through UKOSS, the relevant UKOSS reporting clinician will be contacted and asked to complete a data collection form. In addition, ascertainment of any maternal deaths from PE occurring during the study period will be checked through MBRRACE-UK, the collaboration responsible for the UK Confidential Enquiries into Maternal Death. Where a case is identified, the UKOSS clinician will be contacted and asked to complete a data collection form if appropriate.

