It will not be practicable to obtain consent for data collection from individual women, as this would prevent the achievement of the primary objective of the study, namely to collect information on all confirmed cases of PE in pregnancy in the UK. The National Information Governance Board (NIGB) Confidentiality Advisory Group considers that organisations seeking to use NHS information for research purposes without consent should seek anonymised or pseudonymised data only and not any personally identifiable information. Accordingly, names, addresses, postcodes, dates of birth, NHS or hospital numbers will not be collected in the UKOSS research platform. Women with diagnosed PE will be identified by a member of the clinical care team who will extract anonymised data from the hospital records. Collection of anonymised data in this way in the absence of consent is unlikely to cause significant harm. This UKOSS methodology has received the approval of the London Multi-centre Research Ethics Committee (study reference 04/MRE02/45).

Suspected PE: Clinical staff in the participating hospitals will be asked to prospectively identify any pregnant or post-partum women who require diagnostic imaging for suspected PE or who are in hospital after having received diagnostic imaging for suspected PE. They will provide women with information about the study and then contact the study research nurse, where possible. Research nurses, and appropriately trained clinicians who have completed Good Clinical Practice (GCP) study specific training, and are named in the delegation log will check inclusion criteria and seek informed consent to participate. Participants will be given a patient information sheet to read and approximately one hour to consider whether to take part in the study.

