Diagnosed DVT: Clinical staff in the participating hospitals will be asked to prospectively identify any pregnant or postpartum woman with diagnosed DVT confirmed by imaging, but without suspected PE (who should be recruited as suspected PE). They will provide women with information about the study and then contact the study research nurse, where possible. Research nurses, and appropriately trained clinicians who have completed Good Clinical Practice (GCP) study specific training, and are named in the delegation log, will check inclusion criteria and seek informed consent to participate. Participants will be given a patient information sheet to read and approximately one hour to consider whether to take part in the study.

Multiple presentations: At participating hospitals women will not be recruited to the study more than once with the exception of women included in the Diagnosed DVT group who may re-present as a Suspected PE. These women will be identified and approached in accordance with the Suspected PE group, and will be required to provide the blood sample, regardless of whether a previous sample has been obtained when included in the Diagnosed DVT group.

Women recruited to Suspected PE who have a PE will also be reported by the UKOSS reporting clinician to UKOSS, in these circumstances multiple presentation will be handled in the analysis (p25).

Women who have previously had data collected anonymously in the Non- Recruited will be screened for eligibility to the Suspected PE and Diagnosed DVT group if they represent.

Withdrawal criteria

The only withdrawal criteria are patient request for withdrawal from the study.

5. Assessments and procedures

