5.2 Biomarker study

The case-control study will allow us to evaluate routinely recorded clinical variables, including those constituting existing clinical prediction rules, and current diagnostic tests, such as D-dimer. However, we also plan to evaluate potential alternative biomarkers and undertake more detailed analysis of D-dimer to determine whether a pregnancy-specific threshold could optimise specificity without compromising sensitivity. Patient consent is required to take additional blood samples so the biomarker study will only include women with suspected PE recruited to the prospective study and will not include women with diagnosed PE identified through UKOSS. Since only a small number (~5) will actually have PE, we will augment the sample with pregnant or postpartum women who have DVT diagnosed during the recruitment period at the 8 participating hospitals, thus including all women with diagnosed VTE. There are good pathophysiological reasons for expecting that biomarkers will have the same sensitivity in PE and DVT and empirical studies of D-dimer have shown similar sensitivity in DVT and PE (Stein 2004).

Pregnant or postpartum women with suspected PE recruited to the prospective study will be asked to provide an additional blood sample when blood is taken for routine clinical care. If it is not possible to take the additional sample at the same time as blood sampling for routine care the patient will be asked to provide an additional blood sample, which may require the patient to undergo an additional venepuncture procedure. In addition, we will recruit any women with a DVT diagnosis confirmed by imaging (ultrasound, magnetic resonance, CT or contrast venography) who is willing to provide an additional blood sample. The incidence of DVT in pregnancy and postpartum is around 4 times that of PE (Kane 2013) so we anticipate recruiting around 20 women with DVT. Thus the sample for the biomarker sub-study will include 245 women with suspected PE but negative diagnostic testing, 5 women with diagnosed PE and 20 women with diagnosed DVT (i.e. 25 with VTE).

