Blood samples will be stored and transported for analysis at Guys and St Thomas's (GSTT) Hospital. Analysis will involve (1) comparison of biomarker levels between women with and without thromboembolism, (2) construction of receiving operator characteristic (ROC) curves and calculation of the area under ROC curve, and (3) exploration of the impact of using a pregnancy-specific threshold upon the ROC analysis.

We plan to test the following biomarkers (see Table 4), along with any potential new biomarkers that become available during the project

Table 4: Biomarkers to be tested

Biomarker	Description
D-Dimers (ELISA)	A fibrin degradation product - a small protein fragment
	present in the blood after a blood clot is degraded by
	fibrinolysis. Measured by enzyme-linked immunoassay
	(ELISA) and a highly sensitive assay.
D-dimers (latex	As above, but measured by latex agglutination. This is a
agglutination)	point of care test that is used by many routine
	laboratories
Plasmin-antiplasmin assay	An ELISA assay that measures the level of plasmin-
(PAP)	antiplasmin complexes and thus is a very sensitive assay
	of plasmin activation.
Prothrombin fragment 1+2	A small molecule cleaved from prothrombin when
(PF 1 +2)	thrombin is generated. It is thus a sensitive marker of

	thrombin generation i.e. coagulation turnover. It is an ELISA assay
Thrombin Generation	Thrombin generation can be measured dynamically using the Endogenous Thrombin Potential [ETP], a term introduced by Hemker in 1986 that refers to the total amount of thrombin generated during the test. Commonly measured variables when analysing thrombin generation include the Lag Time, the Time to Peak Thrombin Generation, the Endogenous Thrombin Potential [ETP] - the area under the curve.
Prothrombin time (PT)	A routine measure of the extrinsic pathway of coagulation, used to determine the clotting tendency of blood.
Activated partial thromboplastin time (APTT)	A routine measure of the intrinsic and common coagulation pathways, used to detect abnormalities in blood clotting.
Clauss Fibrinogen	A functional measure of fibrinogen
Soluble Tissue Factor (sTF)	A marker of tissue factor activation - when tissue factor is upregulated part of the molecule enters the systemic circulation.
Troponin I	Part of the troponin complex in cardiac muscle tissue, used to detect myocardial damage resulting from myocardial ischaemia or noncardiac causes such as PE.

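### About four in five of the VTE samples in the biomarker study are taken after diagnosis by design, and anticoagulation at sampling is neither controlled nor listed as an uncertainty

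*Protocol*

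**What the plan says.** **When blood is taken.** The protocol gives three statements:

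- Study Summary (measurement of costs and outcomes): "Research nurses will collect standardised clinical data and a blood sample at enrolment from women with suspected PE".
- Section 5.2: women with suspected PE "will be asked to provide an additional blood sample when blood is taken for routine clinical care", with a separate venepuncture if that is not possible.
- Section 5.1.6: "Blood samples are to be taken prior to hospital discharge".

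**Who can be sampled.** Under Sampling and Informed Consent in section 4, suspected-PE recruitment extends to women "who are in hospital after having received diagnostic imaging for suspected PE". For the DVT group, staff are to "prospectively identify any pregnant or postpartum woman with diagnosed DVT confirmed by imaging". The treatment-related exclusion for that group is "Women who have been diagnosed with PE or DVT earlier in the current pregnancy and are currently receiving treatment". It concerns earlier episodes, not treatment begun for the DVT that brings the woman into the study. A DVT participant who later presents with suspected PE may be recruited again and gives a second sample. Section 6 says that her samples will be flagged as coming from one person, but not which of them is analysed.

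**How the samples are used.** Section 5.2 plans "comparison of biomarker levels between women with and without thromboembolism", ROC curves, and a pregnancy-specific D-dimer threshold. Section 5.3 takes biomarker sensitivities for the model from the roughly 25 VTE women. It carries a marker forward only if its c-statistic is significantly above 0.5 and at least comparable with that of D-dimer. The uncertainties it lists for biomarker sensitivity are imprecision, extrapolation from VTE to PE, and shrinkage from a data-derived threshold.

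**The concern.** A test that selects women for imaging is used before diagnosis and before any treatment that follows from it. Most of the VTE women here are sampled after diagnosis. Several Table 4 markers measure the processes that anticoagulants act on: D-dimer, plasmin-antiplasmin complexes, prothrombin fragment 1+2, thrombin generation, PT and APTT. If treatment has started by the time of sampling, markers of clotting activity could be lower than at presentation. Clotting times could be longer for a reason unrelated to the thrombosis.

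The effect would not cancel if VTE women are treated more often than imaging-negative controls. It would then enter the comparison of levels, the ROC areas, the D-dimer threshold, the choice of markers to model, and the modelled sensitivities. Selection could be affected twice, because D-dimer is both a candidate and the benchmark for the others.

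**Working it through.** **1. The plan's own VTE count.** Inputs: 2% prevalence and 250 women with complete data (section 6), and a DVT incidence about 4 times that of PE (section 5.2).

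- PE: 0.02 × 250 = 5
- DVT: 4 × 5 = 20
- VTE: 5 + 20 = 25, which reproduces the figure in section 5.2.

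**2. Share sampled after diagnosis by design.** All DVT women enter after imaging confirmation.

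- With 5 PE: 20/25 = 80%
- With about 6 PE (section 3.2, recruitment target 325): 20/26 = 77%

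Any PE woman recruited after her imaging adds to this share. The share follows from the DVT entry rule. The section 5.1.6 window only permits the same thing in the suspected-PE group.

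**3. Possible effect on sensitivity (illustration; all inputs assumed except the 20:5 split).** Let pre-treatment sensitivity be 95%, f the fraction of DVT women treated before sampling, and d the fall in sensitivity in those treated. PE women are taken as untreated at sampling.

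Pooled sensitivity = [20 × (0.95 − f·d) + 5 × 0.95] / 25 = 0.95 − 0.8·f·d

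| Fall d | f = 1 | f = 0.5 | f = 0 |
|---|---|---|---|
| 5 points | 91% | 93% | 95% |
| 10 points | 87% | 91% | 95% |
| 20 points | 79% | 87% | 95% |
| 30 points | 71% | 83% | 95% |

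The bias therefore runs from 0 (no DVT woman treated at sampling) through 2 points (f = 0.5, d = 5) to 24 points (f = 1, d = 30).

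**4. Comparison with sampling error.** SE = √(p(1 − p)/n) at p = 0.90:

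- n = 25: √(0.09/25) = 6.0%
- n = 6: √(0.09/6) = 12.2%
- n = 5: √(0.09/5) = 13.4%

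If every woman tests positive, the exact 95% lower limit is 86.3% at n = 25 and 47.8% at n = 5. The last two sample sizes are the worst case for an analysis that drops every woman sampled after treatment, reached if all DVT women are treated before sampling.

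**The case against.** **The window is not wholly open.** A reader might take discharge as the only timing rule. That is not so: the Study Summary and section 5.2 place the suspected-PE sample at enrolment or with routine blood. What stands is that the three statements do not agree. Enrolment itself may also follow imaging in the suspected-PE group, and always does in the DVT group. Tightening section 5.1.6 alone would leave every DVT sample post-diagnosis.

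**Post-diagnosis is not the same as anticoagulated.** A reader might infer that most VTE women are on treatment when sampled and that controls are not. The protocol does not say when treatment starts in either group, so differential exposure is plausible but not shown. What stands is that nothing in the protocol prevents it.

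**Some of this may sit in documents not shown.** Analysis detail is deferred to a separate SAP, and the case report forms are not available, so it cannot be said that time fields are absent. Treatment data are collected for suspected-PE women from the 30-day record review. For the DVT group, section 5.1.4 mentions only a form covering standard clinical assessment. A SAP cannot stratify by times that were never recorded.

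**The DVT augmentation is a deliberate trade-off.** The aim is exploratory, section 5.3 accepts that the biomarker data are limited, and adding DVT women is a reasoned response to having about 5 PE cases. This argues against making an untreated-only analysis primary, and it stands. However, the stated rationale is that sensitivity is similar in DVT and PE, which does not address treatment at sampling.

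**Some results are untouched.** Troponin I, B-type natriuretic peptide and CRP fall outside the coagulation argument. Routine D-dimer in the case-control study is evaluated separately from the stored-sample study.

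**Conclusion.** The point holds as a design weakness with a known structure and an unknown size. That 77% to 80% of the VTE samples are post-diagnosis by design follows from the protocol's own numbers and entry rule. The protocol states sampling time in three ways that need reconciling. It sets no condition on anticoagulation for the current episode and omits treatment at sampling from the uncertainties that section 5.3 will explore.

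The bias itself is conditional on VTE women being anticoagulated at sampling more often than controls, and on treatment shifting the markers. A reader might infer a definite bias larger than the 6.0-point standard error. The documents do not support that: across the assumed range the bias may be below or well above that error. The case for acting is that the plan as written would pool possibly treated cases with controls whose exposure may differ. The resulting accuracy would then feed marker selection and the model without any check.

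**What to change.** 1. Reconcile the Study Summary, section 5.1.6 and section 5.2 on when the study sample is taken, and state the timing for the DVT group.
2. Ensure that the case report form records the time of the study sample and of the first anticoagulant dose for every biomarker participant, including the DVT group.
3. Keep the all-samples analysis. Add a prespecified sensitivity analysis by anticoagulation status and time at sampling, including one that excludes women sampled after treatment.
4. Add treatment at sampling to the uncertainties in biomarker sensitivity explored in section 5.3.
5. For women sampled both as DVT and as suspected PE, use one sample per woman in each analysis and state which one.

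**Cost:** two time fields and a little more analysis. The untreated subgroup may hold only 5 or 6 VTE women, with a standard error of about 12% to 13% at 90% sensitivity, so it can flag a problem but not replace the main estimate. No change to treatment is implied.

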5.1.7 Adverse events

Adverse events are being collected in the study to input into the decision model. As this is a non-interventional study there are no safety reporting requirements.

Research nurses, and clinicians should remain vigilant to possible adverse events as result of the research processes and data collection, this may involve issues from taking an additional blood sample, issues with the venepuncture process, or delays to receiving standard care. Any possible adverse event should be recorded on the adverse event form and reported in accordance with the CTRU SOP (PM004)

5.1.8 Protocol Non-compliance

Protocol non-compliances will be reported as per the Sheffield CTRU SOP: and the process will be agreed with the Sponsor.

Table 3: Data collection

	Where	Completed by	For	mat	When	Which element (s) of the study relevant for	Purpose/Data collected
FORMS AND OUTCOME MEASURES			Paper	Electronic			
Retrospective study: PE cases							
UKOSS card	ED, maternity unit or medical admissions unit	UKOSS nominated clinician	х		Sent once a month throughout study and completed when a new PE case identified	Case control study	To identify cases of PE retrospectively to enable more detailed data collection
Case report form	ED, maternity unit or medical admissions unit	UKOSS nominated clinician	x		Sent in response to the UKOSS nominated clinician indicating that a PE case has been seen	Case control study, decision analytic model	To collect potential predictor variables, diagnostic test results, management and outcomes
Prospective study: Suspected cases of	PE (controls)						
Eligibility criteria form	ED, maternity unit or medical admissions unit	Clinical staff and Research nurse	х		At time of recruitment conversations (face-to-face)	Case control study	To determine eligibility for case control study
Informed consent	ED, maternity unit or medical admissions unit	Clinical staff and Research nurse	х		At time of recruitment conversations (face-to-face)	Case control study	To ensure compliance with the study protocol and GCP
Case report form-prospective study (suspected cases of PE/controls) [Includes data collection for biomarker study (~5 PE cases identified by the prospective study, ~245 suspected PE but negative diagnostic testing and 20 DVT cases)]	ED, maternity unit or medical admissions unit	Clinical staff and Research nurse	х		At recruitment/Baseli ne and at 30 days	Case control study, biomarker study, decision analytic model.	To record details of standard clinical assessment at baseline. To record details of any adverse events and the results of diagnostic investigations for PE. To evaluate potential alternative

Questionnaire to record any additional	Participant's	Participant			30 days after	Decision	biomarkers and undertake more detailed analysis of D-dimer To provide EQ-5D
adverse events, health care received and health utility on the EQ5D.	home	Famopant	X	X	baseline	analytic model	data and an estimate of health care resource use and additional adverse events.
Data collection form	Primary Care	General Practitioner	х		Sent after a non- response to 30 day follow up questionnaire.	Case control study, biomarker study, decision analytic model	Record details of any adverse events, any subsequent Thromboembolic events, and additional diagnostic investigations for PE or therapeutic anticoagulation.oc curring in the 30 days since consent.
Feasibility outcomes							
Number and characteristics of eligible patients approached: screening form	ED, maternity unit or medical admissions unit	Clinical staff and Research nurse	х		At time of recruitment conversations	Prospective cohort feasibility	To inform feasibility of a prospective cohort study
Reasons for ineligibility: screening form	ED, maternity unit or medical admissions unit	Clinical staff and Research nurse	Х		At time of recruitment conversations	Prospective cohort feasibility	To inform feasibility of a prospective cohort study
Reasons for refused consent: screening form	ED, maternity unit or medical admissions unit	Clinical staff and Research nurse	х		At time of recruitment conversations	Prospective cohort feasibility	To inform feasibility of a prospective cohort study
Reasons for attrition: withdrawal form	ED, maternity unit or medical admissions unit	Clinical staff and Research nurse	х		At point of study withdrawal	Prospective cohort feasibility	To inform feasibility of a prospective cohort study
Participant attrition rate:	CTRU	Researcher		х	At report writing stage	Prospective cohort feasibility	To inform feasibility of a prospective cohort

DiPEP: Diagnosis of Pulmonary Embolism (PE) in Pregnancy, v6 02 March 2016

						study
Number of missing values/incomplete cases	CTRU	Researcher	Х	At report writing stage	Prospective cohort feasibility	To inform feasibility of a prospective cohort study
Feasibility of recruiting participating centres	CTRU	Researcher	Х	At report writing stage	Prospective cohort feasibility	To inform feasibility of a prospective cohort study

EDED= emergency department; CTRU=clinical trials research unit

